Limitations and Considerations of the Study Outcome. We recognize that all the approaches for measuring viral suppression and ART adherence are limited. First, viral suppression does not directly measure a behavioral outcome but, rather, the biologic effects of the behavior. Second, the self-report measure is biased and has ceiling effects. Finally, the electronic pill box is limited to data collected from the intervention group. While this is a limitation, providing the electronic pillbox to the standard of care (control group) is likely to bias our intervention effects since this pillbox will, in fact, have intervention effects as we have found from our preliminary findings from our WiseApp trial. We closely considered each of these limitations and have, therefore, decided that this three-pronged (i.e., viral load, self-report, and electronic pillbox) approach which will provide the most rigorous approach to measuring our primary and secondary outcomes of viral suppression and ART adherence.

Mediators

Several mediators are hypothesized to explain the mechanisms through which the intervention is anticipated to improve viral suppression. Hypothesized mediators include: self-efficacy, motivation expectancies, self-regulation skills, and HIV-related stigma. The HIV Medication Taking Self-Efficacy Scale is also used to measure ART adherence self-efficacy, or the confidence to take medications in various situations.¹²⁸ Motivation and outcome expectancies of ART adherence are assessed as three separate dimensions: attitudes, norms, and behavioral intentions to adhere to ART medication.¹¹⁸ Self-regulation skills, which include self-monitoring, goal-setting, and enlistment of self-incentives/plans, are also assessed.¹¹⁹ In prior studies of ART adherence, HIV-related stigma and discrimination have been strongly associated with non-adherence;^{14, 129} thus, we also measure HIV-related stigma.

Moderators

Several moderators are hypothesized to affect the strength of the intervention to yield improvements in viral suppression and will be explored. Hypothesized moderators include: depression, anxiety and substance use.

Table 4. Measures and Schedule of Events

	Screening	Baseline	6 mos	12 mos
Sociodemographic: (e.g., age, race/ethnicity, education, housing)		X		
Primary Outcome Measures				
Viral Load through a blood draw	X		X	X
Secondary Outcome Measures				
ART adherence (SRSI) ¹⁰¹ and the CleverCap (intervention group only)	X		X	X

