Additional Outcome Measures				
Quality of Life (PROMIS-29) ¹¹⁵	X	X	X	
HIV Symptom Index ¹¹⁶	X	X	X	
Engagement in HIV Care ¹¹⁷		X	X	X
Mediators				
The HIV Medication Taking Self-Efficacy Scale		X	X	X
Motivation and outcome expectancies of ART adherence are assessed as three separate dimensions: attitudes, norms, and behavioral intentions to adhere to ART medication ¹¹⁸		X	X	X
Self-regulation skills, which include self-monitoring, goal-setting, and enlistment of self-incentives/plans ¹¹⁹		X	X	X
HIV-regulated Stigma ¹²⁰		X	X	X
Moderators				
Alcohol, Smoking & Substance Involvement Screening Test (ASSIST) ¹⁰⁹		X	X	X
Depression and Anxiety (Beck Symptom Inventory) ¹²¹⁻¹²⁴		X	X	X

Depression and anxiety will be measured through the Brief Symptom Inventory, a multi-item scale of mental health in the last seven days that gives a global index and nine primary symptom domains, including depression and anxiety ($\alpha > 0.80$). Problem alcohol and drug use are also assessed with the Alcohol, Smoking & Substance Involvement Screening Test (ASSIST).¹³⁰ The ASSIST consists of nine items, covering ten substances (used in the past four months), including: tobacco, alcohol, cannabis, cocaine, stimulants, inhalants, sedatives, hallucinogens, opioids, and other drugs. The ASSIST assesses frequency of use and associated problems for each substance with good to excellent reliability and validity.

Other Important Outcomes

Quality of life will be measured through the PROMIS-29, an NINR Common Data Element, and an instrument which was validated by [name] for use with PLWH.¹¹⁵ HIV symptoms and management will be measured with the HIV Symptom Index¹¹⁶ and Engagement in HIV Care¹¹⁷ will also be recorded at all assessment points. The blood draw at baseline will also be tested for genotyping, GSA chip and qPCR, hormone blood levels (Estrogen and FSH), and cytokine blood levels (IL-1 β , IL-2, IL-4, IL-6, IL-8, IL-10, IL-13, TNF α , and CRP). The genotyping with GSA chip and qPCR, cytokine blood level and CRP, and hormone blood tests will only be collected once during the course of the study, at Baseline or at the 12-month follow-up if not completed at Baseline. The genotyping, GSA chip and qPCR will be performed by the Feinstein Institute for Medical Research at Northwell Health.

Data Analysis

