Efficacy: The impact of an intervention on outcomes including potential negative effects, quality of life.	
Did the intervention achieve primary and secondary outcomes?	Between-group comparisons on primary and secondary outcomes (Aim 1)
Did it produce unintended adverse consequences?	Review notes from participant study withdrawal, Notifications to the IRB about participant complaints
What effect did the mediators and moderators have on the primary and secondary outcomes?	Data analyzed in Aim 2
Adoption: The absolute number, proportion, and acceptability of CHAMPS; proportion of eligible patients that enroll.	
Did the intervention help the organization address its mission, values, and priorities?	Key informant interviews with clinic staff, research staff, CHW, and administration - descriptive, interpretative analysis for key themes
Implementation: At the setting level, includes consistency of delivery and predisposing, enabling, and reinforcing factors. At the individual level, implementation refers to individual's use of strategies. ¹⁵²	
Were intervention components delivered as intended?	Paradata Analysis –App use by component
What barriers to implementation were identified and how were they addressed?	Key informant interviews with study staff; In-depth interviews with study participants. - descriptive, interpretative analysis for key themes
What enabling (facilitating) factors were required to support the intervention?	Project meeting minutes Interviews with stakeholders
Maintenance: Individual – Understanding Use of the App over time.	
Did the intervention produce lasting effects at individual level?	Long-term efficacy of CHAMPS intervention over 12 months
Is there the potential for sustaining CHAMPS over time?	Key informant interviews with clinic staff, research staff, CHW and clinicians, CBO staff and study participants.
How did the intervention evolve?	Project meeting minutes; Paradata

implementation evaluation for this proposal; [name] will provide oversight, along with MPIs [name] and [name], for all implementation activities.

Process Evaluation Outcomes

The RE-AIM evaluation dimensions and associated measures in our study are summarized in Table 5. In addition to testing the **Efficacy** of CHAMPS, we will concurrently measure the four remaining RE-AIM dimensions¹⁵¹ as follows:

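### Table 4 schedules PROMIS-29 and the HIV Symptom Index at screening, baseline and 6 months but not at 12 months, so neither has a 12-month comparison if the table is followed.

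*Combined protocol and SAP*

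**What the plan says.** Table 4, "Measures and Schedule of Events", has four columns: screening, baseline, 6 months and 12 months. PROMIS-29 and the "HIV Symptom Index" stand there as additional outcomes, each marked in the first three columns and blank in the fourth. The next row, "Engagement in HIV Care", is marked at baseline, 6 and 12 months.

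The text under Other Important Outcomes names the quality-of-life instrument ("Quality of life will be measured through the PROMIS-29, an NINR Common Data Element") and attaches no visits to it. The following sentence says that symptoms are measured with the Symptom Index and continues that Engagement in HIV Care "will also be recorded at all assessment points".

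The Procedures section plans visits in both arms at screening, baseline, 6 months and 12 months. The Randomization section places allocation after the baseline assessment. Table 5 defines the RE-AIM Efficacy dimension as "The impact of an intervention on outcomes including potential negative effects, quality of life". Under Maintenance it asks whether effects on individuals last, to be answered by "Long-term efficacy of CHAMPS intervention over 12 months".

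**The concern.** The intervention lasts six months, followed by six further months of observation. Month 6 is therefore the end-of-intervention visit, and month 12 is the only planned visit that can show whether an effect persists. A site working from Table 4 would give these two questionnaires twice before allocation, once at the end of the intervention, and not at the later visit that participants attend anyway. No reason for leaving out month 12 is given. Patient-reported data not taken at that visit cannot be reconstructed afterwards, whereas an inconsistency in the analysis text could still be resolved once the data are in.

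**Working it through.** The plan gives no figure to reproduce. The check is a count of the Table 4 marks, set against the text.

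**1. Marks by row**

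| Rows in Table 4 | Screening | Baseline | 6 mo | 12 mo | Before / after randomisation |
|---|---|---|---|---|---|
| Viral load; ART adherence (2 rows) | X | | X | X | 1 / 2 |
| PROMIS-29; HIV Symptom Index (2 rows) | X | X | X | | 2 / 1 |
| Engagement in HIV Care (1 row) | | X | X | X | 1 / 2 |
| Mediators (4 rows) | | X | X | X | 1 / 2 |
| Moderators (2 rows) | | X | X | X | 1 / 2 |

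That makes 2 + 2 + 1 + 4 + 2 = 11 outcome, mediator and moderator rows. Nine have a 12-month mark. The two that do not are also the only two marked at both screening and baseline. All 11 rows carry three marks, so the two exceptions look like the usual questionnaire pattern moved one column to the left.

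**2. Table against text, Symptom Index.** The sentence couples the Symptom Index with Engagement in HIV Care and then refers to all assessment points. Engagement itself has no screening mark, so the phrase appears to mean baseline, 6 and 12 months. Whether it means those three visits or all four, it includes month 12. If it covers the Symptom Index, the table and the text disagree at month 12.

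**3. Table against text, PROMIS-29.** The text gives no visits, so there is nothing to contradict. Table 4 is the only place from which a site could take the timing.

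**4. Number of assessments at issue.** Inputs are 300 participants and 80% retention at each follow-up (Sample Size and Power Calculation), which agrees with the 20% attrition to month 12 in the Aim 1 Data Analysis section.

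300 x 0.80 = 240 month-12 assessments per instrument.

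This is an upper figure. It applies only if the table is followed as it stands.

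**5. After the correction.** With marks at baseline, 6 and 12 months, each instrument has one value before randomisation and two after. It is still given three times per participant.

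**The case against.** Four arguments stand on the other side.

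- **The layout may be an artefact.** Losing one leading empty cell in each of two adjacent rows when the table is converted from PDF would produce this pattern. That cannot be excluded. It is not the likelier reading, because the same table keeps leading blanks (mediators, moderators, Engagement), an internal blank (viral load, adherence) and trailing blanks (sociodemographic items). A slip in the table itself is plausible. A look at the source table settles it.
- **The conflict with the text is limited.** A reader might infer that the text contradicts the table for both instruments. It does not do so for quality of life, where no timing is stated. For the Symptom Index, strict grammar could confine the phrase to Engagement in HIV Care. If the phrase does cover the Symptom Index, the text already requires month 12, and the data are lost only if sites follow the table instead.
- **Aim 1 does not promise these outcomes at 12 months.** A reader might infer that it does. Its 6- and 12-month assessment names viral suppression and ART adherence, and the sustainability test concerns viral suppression. Quality of life and symptoms are additional outcomes without a hypothesis or power statement. The link of quality of life to 12 months is indirect: it appears in the definition of RE-AIM Efficacy, and the Maintenance row lists no outcomes.
- **A post-randomisation comparison remains.** A reader might infer that no between-arm comparison is possible once the intervention has ended. Both instruments are marked at 6 months, so an end-of-intervention comparison survives. Only persistence at month 12 is lost.

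These points limit the claim without removing it. The schedule still differs from every comparable row without explanation, and it is the document that sites are likely to work from.

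**Conclusion.** The point holds as a scheduling inconsistency with a real but limited consequence. As Table 4 stands, PROMIS-29 and the HIV Symptom Index have two pre-randomisation values, one at month 6 and none at month 12. If the table is followed, the arms can be compared on these measures at month 6 only. The RE-AIM question on lasting effects then cannot be answered for quality of life or symptoms, and up to about 240 assessments per instrument are not collected.

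This rests on three assumptions: that the marks read here are those of the source table, that sites follow the table over the text, and that retention at month 12 is the planned 80%. Nothing in the primary outcome, its power calculation or its analysis changes. The documents do not support calling this a failure of Aim 1, nor a contradiction between table and text for quality of life. It deserves correction because the change is nearly free and the missing data would be irrecoverable.

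**What to change.** - Check the two rows against the source table; a one-column shift is likely.
- Mark PROMIS-29 and the HIV Symptom Index at baseline, 6 and 12 months, as for the other questionnaires.
- Under Other Important Outcomes, state the PROMIS-29 visits, and reword the next sentence so that the timing plainly applies to both the Symptom Index and Engagement in HIV Care.
- In the Aim 1 Data Analysis section, the mixed models are extended to secondary outcomes, and these two measures are not named. State that the same models apply to them, with between-arm comparisons at months 6 and 12.
- If month 12 was left out on purpose, say so, give the reason, and make no 12-month claim for quality of life or symptoms, including under RE-AIM Maintenance.

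The cost is a correction to one table and two short text edits. A few minutes of questionnaire time move from screening to a 12-month visit that already takes place in both arms, and the second pre-randomisation measurement is given up. The total number of administrations does not change.

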We have estimated the statistical power for the primary outcome of viral suppression (viral load ≤ 200). We will recruit and enroll 300 participants (n=150 in each site) and use a 1:1 random assignment to the intervention arm and the control arm (i.e., 75 in each arm per site). We estimate the statistical power to examine efficacy of the intervention at six months for the total subjects. All power estimations are based on $\alpha=0.05$ and 2-sided tests and following assumptions: (1) an 80% retention rate, at each follow-up assessment for each study arm (based on our 86.1% retention rate in New York City WiseApp trial); (2) a correlation of 0.6 of outcome measure for participants at different time points of assessment; (3) an intra-cluster correlation (ICC) of 0.2 of participants of same study sites; and (4) 75% baseline viral suppression rate (based on preliminary data of the BA2C study).

For the total sample (n=300), the proposed study will have at least 80% power to detect a difference of 12% or greater in viral suppression. The 12% difference in viral suppression is equivalent to a small effect size (Cohen's D of 0.31). Therefore, the proposed study will have sufficient power ($\geq 80\%$) to detect a small effect size or greater. Based on findings from our BA2C and WiseApp interventions, we expect a combined improvement of 12% on viral suppression as compared to the control arm.

We have also estimated the statistical power to assess sustainability of the intervention at 12 months. For this analysis, we will conduct a non-inferiority test of viral suppression at Month 12 as compared to Month 6. This study will have at least 80% power to conduct a non-inferiority test with a margin of 10%.

Sampling approach to successfully enroll PLWH who are not optimally engaged in HIV Care: Using active and passive recruitment methods, the project coordinator at each site will oversee and participate in recruitment efforts. The study staff hired through this project and the peer-to-peer networking efforts at each site will be used to recruit study participants. Our study team at both sites has extensive experience in recruitment efforts for projects similar to the one proposed here and will be able to successfully recruit the study sample.

Eligibility Screening

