Potential participants will either call, text, or email the study team via the advertised phone number or email address or, if contact information is gathered at the recruitment venue, be called, texted, or emailed by project staff. Screening will be conducted over the phone, in person for walk-ins, or electronically via REDCap. Each potential participant will be screened for eligibility based on the inclusion/exclusion criteria. Participants who do not have a recent (≤ 8 weeks) available viral load test result will need to complete a study blood draw.

Participants may also sign a Release of Information (ROI) form, in-person or remotely, to allow study staff to access their electronic medical record (EMR) and determine eligibility based on past "no-show" visits. Forms completed electronically will be conducted via video conferencing such as Skype, Zoom, FaceTime using REDCap to collect the e-ROI and answer participant questions. Through the REDCap platform, participants will

be able to securely download a copy of the e-ROI for their records. As part of the REDCap e-consent platform e-ROIs will be automatically archived and securely stored in REDCap. If deemed eligible, staff will work with the potential participant to schedule an enrollment visit at a convenient time for the participant.

Randomization

Using the randomization approach described below, there will be random or minimally biased assignment of subjects to study arms. Randomization will be achieved through a blocked design utilizing permuted blocks of random sizes. The design ensures equal representation of treatment assignment across groups and protects the study team and investigators from easily anticipating treatment allocation.¹⁰⁷⁻¹¹⁰ Randomization to *CHAMPS* or standard of care is 1:1. Participants will be randomized using computer-generated random numbers at baseline. The randomization database will be stored on a password protected computer at Columbia University and will only be accessible to MPI [name] to avoid the possibility of the study sites subverting randomization as has been noted in previous studies.¹¹¹ Following completion of the informed consent and baseline assessment, participants will be randomly assigned to one of two trial arms using sequentially numbered, opaque, sealed envelopes containing the intervention assignment, which the staff member opens at the moment of randomization.¹¹²

Procedures

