Data will be electronically collected, managed, and secured using REDCap™ by study staff trained on REDCap data entry, management, and security.¹²⁵ Quality assurance measures, including built-in skip patterns, validation ranges, and logic checks, minimize data collection and data capturing errors. Quality control measures, including internal monitoring systems and daily and weekly reporting, are run to ensure expedient error correction and to optimize data integrity.

Study Outcomes

The study outcomes are described in Table 4. The primary outcome of the study is viral suppression which will be operationalized as viral load ≤ 200 at 6 months. Viral load is the biologic correlate of the ART adherence behavior; yet, to achieve biologic change, there must be change in the adherence behavior. As suggested through the “Undetectable equals Untransmittable,” or “U=U,” public health campaign,^{126, 127} PLWH who take ART as prescribed and achieve and maintain viral suppression have effectively no risk of sexually transmitting the virus to an serodiscordant partner.¹²⁸ Our secondary and related outcomes include ART adherence measured in two ways: 1) a single-item self-report measure, an empirically validated instrument,¹⁰¹ and 2) electronic pill bottle data, collected via the CleverCap bottle. The electronic

pill bottle data provide a less subjective measure as compared to self-report. We will also measure missed healthcare visits using electronic medical record (EMR) data.

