The distribution of all variables will be assessed, as will the correlations between all variables and the primary/secondary outcomes. We will assess for patterns of missing data, which are expected to be low as the study utilizes computer-assisted self-interview (CASI) for sensitive data, which reduces participant nonresponse. The primary anticipated reason for missing data is attrition due to loss to follow-up. Based on our preliminary studies, we are accounting for 20% attrition from randomization to the 12-month assessment.

All multivariate analyses will be preceded by standard descriptive bivariate analyses to describe key variables and relationships among them. These analyses will include means, frequency tables, histograms, and examination of distributions. All statistical tests will be two-sided tests with the level of significance at 0.05. The primary hypothesis 1 will be a comparison of viral suppression (primary outcome) between CHAMPS and standard of care. We will also compare the drop in viral load (measured in logarithmic scale with base 10) between the two groups. Our secondary and related outcome is ART adherence measured in two ways: 1) a single-item self-report measure, an empirically validated instrument (SRSI)¹⁰¹ and 2) electronic pill bottle data which we will be collecting in the intervention group since all participants will receive a CleverCap bottle for their medications. All the analyses will be based on initial assignment to groups, using the intention-to-treat principle.^{131, 132}

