The primary hypothesis 1 (H_1) will be tested using a generalized linear mixed model (GLMM) with logit-link function for binary outcomes (i.e., viral suppression) or a linear mixed model (LMM) for continuous outcomes (i.e., viral load measured in logarithmic scale) to account for the non-independence of repeated measurements within individuals.¹³³ The models will include a random intercept and fixed effects for intervention group, time, and interaction term of group and time which is for testing efficacy of the intervention. The model may include stratification variables, such as study site, age, and sex as covariates. A site by group interaction will be also examined and included in each model (above) if significant at the .05 level. All analyses will be tested for goodness-of-fit using the Wald-type test, which shows satisfactory performance for models with fewer (<5) covariates.¹³⁴ A similar GLMM will be used to test sustainability of the intervention at month 12. For this analysis, we will conduct a non-inferiority test¹³⁵ to compare viral suppression rate between month 12 and month 6. For primary hypothesis 2 (H_2), testing for intervention effect on ART adherence measured by SRSI (secondary outcome), we will use a similar LMM as mentioned above. For electronic pill bottle data in the intervention group, we will also examine the trend of electronic pill bottom data over time with a GLMM which will include a first-order autoregressive (AR1) covariance structure, as described by Hedeker and Gibbons.¹³³ We will also aggregate the electronic pill bottle data at different time points (0, 6, and 12 months) and examine the association between the electronic pill bottle data and ART adherence data measured by SRSI using Spearman nonparametric correlation.¹⁰¹ Similar GLMMs or LMMs will be used for secondary outcomes, with GLMMs for binary outcomes and LMMs for continuous outcomes.

Aim 2: Identify mediators and moderators of CHAMPS on study outcomes.

Data Analysis

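### The primary group-by-time test estimates a baseline arm difference that randomisation makes zero in expectation; a common-baseline month-6 contrast typically gains 4 to 8 points of power at no cost

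*Combined protocol and SAP*

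**What the plan says.** The Study Outcomes section defines the primary endpoint as suppression "operationalized as viral load ≤ 200 at 6 months". The Aim 1 Data Analysis section tests it in a random-intercept, logit-link mixed model that has "fixed effects for intervention group, time, and interaction term of group and time which is for testing efficacy of the intervention". Possible covariates named are site, age and sex. Pre-randomisation viral load or suppression status is not among them. The section does not say whether time is categorical, which visits enter, or which coefficient is the primary test.

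Baseline as a time level is implied but not written:

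- Table 4 schedules viral load at screening, 6 and 12 months.
- The Sample Size section assumes a 75% baseline suppression rate and "a correlation of 0.6 of outcome measure for participants at different time points of assessment".
- The same Data Analysis section adds: "We will also compare the drop in viral load (measured in logarithmic scale with base 10) between the two groups".
- Under Eligibility Screening, "Participants who do not have a recent (≤ 8 weeks) available viral load test result will need to complete a study blood draw", so everyone should have a viral load before randomisation.

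The power statement is "at least 80% power to detect a difference of 12% or greater in viral suppression" for 300 participants. It also assumes 80% retention and "an intra-cluster correlation (ICC) of 0.2 of participants of same study sites".

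**The concern.** If only months 6 and 12 were time levels, the interaction would measure how the arm difference changes after month 6, not efficacy at month 6. So baseline has to be a level. The month-6 interaction is then the month-6 arm difference minus the baseline arm difference. The Randomization section places assignment after the baseline assessment, so the expected baseline difference is zero. The free group main effect makes the model estimate it anyway, and its sampling error passes into the efficacy test.

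No bias or inflation of type I error follows. What is lost is power, in a trial whose stated power leaves little reserve. The information needed to recover it is already being collected.

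**Working it through.** **Inputs.** From the Sample Size section: two-sided 0.05; 150 per arm; 80% retention, so m = 120 per arm at month 6; a pre-randomisation value for all n = 150; correlation ρ = 0.6; site ICC 0.2; 75% baseline rate; a 12-point difference, hence 75% versus 87%. Assumptions not in the plan: control stays at 75%, and missingness is completely at random.

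**The plan's own figures.** On the arcsine scale the effect is h = 2·asin(√0.87) − 2·asin(√0.75) = 0.309, matching the stated 0.31. The plan gives no power formula. On this scale (unit variance), candidates are:

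- Month 6 only: variance 2/120; power 66.9% (66.1% by the two-proportion formula). This does not reproduce 80%.
- Change score in completers: variance factor 2(1 − 0.6) = 0.8; power 76.4% (75.7% with pooled proportions).
- Mixed-model interaction, as below: 78.1%, or 86.4% with site variance removed. These bracket the stated 80%.

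**Interaction against common baseline (two visits, known covariance).**

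- Interaction: variance = 2[(1 − ρ²)/m + (1 − ρ)²/n] = 2[0.64/120 + 0.16/150] = 0.01280. SE 0.1131; h/SE = 2.735; power = Φ(2.735 − 1.96) = 78.1%.
- Common baseline: variance = 2(1 − ρ²)/m = 2(0.64/120) = 0.01067. SE 0.1033; h/SE = 2.996; power = Φ(2.996 − 1.96) = 85.0%.
- The variance ratio is 0.01280/0.01067 = 1.20, so the interaction needs about 20% more participants for equal precision, roughly 60 on 300.
- Multiplying both variances by 1 − 0.2 for site gives 86.4% and 91.8%.

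**Sensitivity to the correlation (same formulas, no site factor).**

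| ρ | Interaction | Common baseline | Gain (points) |
|---|---|---|---|
| 0.4 | 61.7% | 74.4% | 12.7 |
| 0.6 | 78.1% | 85.0% | 6.9 |
| 0.7 | 88.1% | 91.9% | 3.7 |
| 0.8 | 96.9% | 97.9% | 1.0 |

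**Simulation of the planned model.** Random-intercept logit, visits 0, 6 and 12, 20% missing at each follow-up, month-12 effect assumed equal to month 6, 4,000 runs per case (error of a paired gain 0.5 to 0.6 points). Power in %; gains over the interaction, in points, are differences of the rounded figures.

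| Data-generating case | Interaction | Common baseline | Month-6 logistic adjusted for baseline suppression | Gains |
|---|---|---|---|---|
| 1. Latent normal, binary correlation 0.6 | 78.4 | 84.5 | 82.8 | 6.1; 4.4 |
| 2. Random-intercept logit, 0.6 | 77.4 | 83.0 | 82.0 | 5.6; 4.6 |
| 3. Person-level beta probabilities, 0.6 | 68.3 | 75.6 | 79.0 | 7.3; 10.7 |
| 4. Correlation decaying over visits | 75.2 | 82.2 | 82.8 | 7.0; 7.6 |
| 5. Case 1 plus site ICC 0.2, site in all models | 82.0 | 87.8 | 86.4 | 5.8; 4.4 |
| 6. 0.6 taken as a latent correlation (binary 0.38) | 62.0 | 73.6 | 72.1 | 11.6; 10.1 |

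Under the null (cases 1, 3, 5 and 6), rejection was 4.6 to 5.1% for the interaction, 4.6 to 4.9% for common baseline and 4.5 to 5.1% for the adjusted logistic model.

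**Same parameter.** In case 1 the mean month-6 log odds ratio was 2.03 under both mixed models, with SD 0.78 for the interaction and 0.73 for common baseline. In case 2, where the mixed model is the true model, both means were 1.99. The adjusted logistic model targets a different odds ratio (mean log 1.25 in case 1).

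**Other readings of the interaction.** In case 1, a two-degree-of-freedom joint test had 83.1% power against 91.6% for its common-baseline version. A linear-time interaction had 83.8% against 92.0%.

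**The case against.** A group-by-time interaction in a random-intercept model is a standard, valid longitudinal analysis, and it fits the planned comparison of the drop in viral load. It already uses the baseline data. Once the site correlation is included, the planned test exceeds 80% (86.4% by formula, 82.0% by simulation), so the plan's own claim is met without any change. In cases 3 and 6, by contrast, planned power is well below 80%, so describing it as near 80% fits the plan's assumptions only. The premise that baseline is a time level is inferred. The gain depends on the 0.6 correlation and on 75% being suppressed at baseline, although the aims and the Human Subjects section describe participants as virally unsuppressed. Finally, this alters the primary test, which is not trivial in a document dated 05/23/2023 that does not state enrolment status.

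Most of this stands as qualification. The change is optional, the size is conditional, and timing matters. None of it shows the interaction to be as efficient as the alternative. The inferred premise does not rescue the plan either: without a baseline level the interaction would not test the stated endpoint, so the wording needs completing on either reading.

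**Conclusion.** The point holds as an efficiency gain worth taking; the planned test is valid. At the plan's assumptions the gain is typically 4 to 8 points, with similar results from the closed-form calculation and the simulations. The span of roughly 0.5 to 12 points describes the settings examined and is not a bound: at a correlation of 0.4, a calculation on the raw risk-difference scale gave about 17. Nothing is claimed about how the gain changes if fewer than 75% are suppressed at baseline. If nobody were suppressed, the binary baseline would carry no information, although log10 viral load might. The common-baseline model keeps the same odds-ratio parameter and showed no type I error cost.

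**What to change.** In the Aim 1 Data Analysis section:

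1. Name the month-6 CHAMPS versus control contrast as the primary test.
2. Preferably take it from the same mixed model with categorical visit effects and arm-by-visit terms at months 6 and 12, but no group main effect at baseline. State that the pre-randomisation (screening) viral load is the baseline value.
3. Alternatively, use a month-6 logistic model adjusted for pre-randomisation suppression or log10 viral load, saying openly that this odds ratio is a different one. Choose one option in advance.
4. Report the standardised month-6 risk difference with a 95% confidence interval, so that the result is on the scale of the 12% in the power section.
5. Keep the planned interaction as a sensitivity analysis.

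For the preferred option the cost is wording only: same data, same model family, same parameter. The change should be dated and justified before anyone sees outcome data by arm.
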